5.9 Changes to Planned Analyses

Any changes to the planned statistical analyses made prior to performing the analyses will be documented in a Statistical Analysis Plan approved prior to performing the analyses.

6 VALIDATION

All clinical data reports generated per this plan will be validated per Global WI: Clinical Data Reporting Validation.

7 PROGRAMMING CONSIDERATIONS

7.1 Statistical Software

All statistical analyses will be done using The SAS System software, version 8 or higher (Copyright © 2000 SAS Institute Inc., SAS Campus Drive, Cary, North Carolina 27513, USA. All rights reserved). For the primary endpoint analysis, StatXact 9® software can be used since SAS does not provide exact non-inferiority analysis as of the writing of this SAP.

7.2 Format of output

Results of analysis will be output programmatically to Word documents from SAS with no manual intervention. All output for the final statistical report will be in the form of a Word document containing tables, figures, graphs, and listings, as appropriate.

7.3 Rules and Definitions

Binary event rates (proportions) will be reported on a per patient basis.

The last follow-up date will be the latest of the following dates for each patient: date of an adverse event, index procedure date, follow-up visit date, any stent procedure/reintervention date, surgery date, stent removal date, and device event date.

Serious Adverse Event will be defined as an adverse event that:

- Led to death
- Led to a serious deterioration in the health of the subject that either resulted in:
 - a life-threatening illness or injury, or
 - a permanent impairment of a body structure or a body function, or
 - in-patient hospitalization or prolonged hospitalization (of an existing hospitalization), or
 - medical or surgical intervention to prevent life-threatening illness or injury or permanent impairment to a body structure or a body function

- Led to fetal distress, fetal death, or a congenital abnormality or birth defect.

Note: Planned hospitalization for a pre-existing condition, or a procedure required by the protocol, without serious deterioration in health, is not considered a serious adverse event.

Successful pre-operative biliary drainage defined as absence of reinterventions for the management of biliary obstructive symptoms.

- For patients undergoing surgery: from stent placement until surgery
- For patients transitioning to palliative management: from stent placement until transition to palliation

Definitions of complication criteria (per van der Gaag article):

Specific PBD (ERCP, PTC) related:

- **Acute pancreatitis** Abdominal pain and a serum concentration of pancreatic enzymes (amylase or lipase) three or more times the upper limit of normal, that required more than one night of hospitalization
- **Acute cholecystitis** No suggestive clinical or radiographic signs of acute cholecystitis before the procedure and if emergency cholecystectomy is subsequently required
- **Perforation** Retroperitoneal or bowel-wall perforation documented by any radiographic technique or direct visual evidence
- **Stent Occlusion** Recurring obstructive jaundice with necessary stent replacement

Specific surgery related:

- **Pancreaticojejunostomy leakage** Drain output of any measurable volume of fluid on or after postoperative day 3 with an amylase content greater than 3 times the serum amylase activity, graded according to clinical course (ISGPS grade A, B, C), or direct visual evidence of defect at anastomosis
- **Delayed gastric emptying** Gastric stasis requiring nasogastric intubation for 10 days or more, or the inability to tolerate a regular (solid) diet on or before the fourteenth postoperative day, not due to sequelae of intra-abdominal complications (i.e. abscess, anastomotic leakage)
- **Biliary leakage** Bilirubin in abdominal drain or dehiscence found at laparotomy
- **Gastro-/duodenajejunostomy leakage** Conclusive radiographic or direct visual evidence of a defect of the anastomosis
- **Intra-abdominal abscess formation** Intra-abdominal fluid collection with positive cultures identified by ultrasonography or computed tomography, associated with persistent fever and elevations of white blood cells

- **Wound infection** Requiring intervention otherwise considered as minor complication
- **Portal Vein Thrombosis** Conclusive radiologic evidence of thrombosis

Following either procedure:

- **Cholangitis** Elevation in temperature more than 38°C, thought to have a biliary cause, without concomitant evidence of acute cholecystitis, requiring intervention
- **Hemorrhage** Bleeding after the index procedure requiring transfusion of ≥ 4 units of packed cells within a 24-hour period, or leading to relaparotomy/intervention
- **(Emergency) (re)laparotomy** Any (other) reason following either preoperative biliary drainage or another surgical procedure
- **Pneumonia** Pulmonary infection with radiological confirmation and requiring antibiotic treatment
- **Mortality** In-hospital death, due to protocol complications or any cause, including progression of disease, within the study period

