### 7.13. *Study Completion*

End of study will be reached at:

- Up to 30 days post-surgery for those patients undergoing potential curative intent surgery
- 1 year post stent placement for patients that have transitioned to palliation within 12 months after stent placement
- 1 year post stent placement for patients who do not undergo potential curative intent surgery and do not transition to palliation within 12 months after stent placement (with or without Neoadjuvant Therapy)

End of study will be reached at study completion, at patient withdrawal from study, or at death, whichever comes first.

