**Table 4: Adverse Event Definitions**

Term	Definition
	applicable, see MEDDEV 2.7/3 12/2010 for reporting timeline requirements.
Unanticipated Adverse Device Effect (UADE)  Ref: 21 CFR Part 812	Any serious adverse effect on health or safety or any life-threatening problem or death caused by, or associated with, a device, if that effect, problem, or death was not previously identified in nature, severity, or degree of incidence in the investigational plan or application (including a supplementary plan or application), or any other unanticipated serious problem associated with a device that relates to the rights, safety, or welfare of subjects.
Unanticipated Serious Adverse Device Effect (USADE)  Ref: ISO 14155-2011	Serious adverse device effect which by its nature, incidence, severity, or outcome has not been identified in the current version of the risk analysis report.  Note: Anticipated serious adverse device effect (ASADE) is an effect which by its nature, incidence, severity or outcome has been identified in the risk analysis report.
Device Deficiency  Ref: ISO 14155-2011  Ref: MEDDEV 2.7/3 12/2010	A device deficiency is any inadequacy of a medical device with respect to its identity, quality, durability, reliability, safety or performance.  Note: Device deficiencies include malfunctions, misuse or use errors, and inadequate labeling.  Note: All device deficiencies that could have led to a SADE if suitable action had not been taken or if circumstances had been less fortunate shall be reported as required by the local IRB/EC, national regulations, or the protocol. If applicable, see MEDDEV 2.7/3 12/2010 for reporting timeline requirements.

Abbreviations: EC=Ethics Committee; IRB=Institutional Review Board

Underlying diseases are not reported as AEs unless there is an increase in severity or frequency during the course of the investigation. Death should not be recorded as an AE, but should only be reflected as an outcome of a specific SAE (see **Table 4** for AE definitions).

All device-related events and all surgery related events experienced by the study patient after informed consent, whether during or subsequent to the procedure, must be recorded in the eCRF.

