3.1.3 Statistical Methods

The distribution of prognostic factors between patients with and without data will be examined on the primary endpoint. Statistical models that account for censored data may be employed in appropriate circumstances, e.g. for time-to-event outcomes. Sensitivity analyses will be conducted to assess the impact of missing data on the interpretation of the results, e.g. a tipping point analysis.

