5 ADDITIONAL DATA ANALYSES

5.1 Secondary Endpoints

1. Occurrence and severity of adverse events related to the stent and/or stenting procedure
2. Occurrence and severity of surgical complications
3. Occurrence and severity of peri-surgical complications (up to 30 days after surgery)
4. Ability to deploy the stent in satisfactory position across the stricture (Stent Placement Success)
5. Improvement of biliary obstructive symptoms during stent indwell at Week 1 and Monthly until surgery or transition to palliation as applicable, compared to Baseline
6. Improvement of Laboratory Liver Function Tests (LFTs) until surgery for patients undergoing surgery, and at Week 1 and Monthly until transition to palliation, and at 1 year after stent placement for patients not undergoing surgery
7. Biliary Reintervention rate
8. Ability to complete neoadjuvant therapy as intended without stent related interruptions of neoadjuvant therapy
9. Stent migration rate
10. Assessment by surgeon of interference, if any, of SEMS on time to surgery and/or success of pancreaticoduodenectomy
11. For patients transitioning to palliative management: Successful biliary drainage defined as absence of reinterventions for the management of biliary obstructive symptoms from stent placement to 1 year after stent placement

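### The SAP's last follow-up date omits death and withdrawal, so any time-to-event analysis that uses it would cut follow-up short after palliation and tend to overstate reintervention risk

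*SAP*

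**What the plan says.** SAP 7.3 gives the rule as a list: "The last follow-up date will be the latest of the following dates for each patient: date of an adverse event, index procedure date", the follow-up visit date, then "any stent procedure/reintervention date, surgery date, stent removal date, and device event date". No date of death, withdrawal or last contact appears. This is the only end-of-follow-up date that the SAP defines, and the SAP does not say which analyses use it.

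Protocol 7.13 closes a patient's study differently: "End of study will be reached at study completion, at patient withdrawal from study, or at death, whichever comes first".

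Other provisions that bear on the rule:

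- **Visits.** Protocol 7.7 schedules week 1 and monthly visits until surgery or transition to palliation. After transition, protocol 3.1 and Table 3 schedule only the 1-year visit. Reintervention visits are as needed.
- **Deaths.** Protocol 10.1 says: "Death should not be recorded as an AE, but should only be reflected as an outcome of a specific SAE". Sections 10.2 and 10.3.2 say that unrelated adverse events are not collected, while the opening of 10.3 asks for every SAE.
- **Analyses.** SAP 7.3 says: "Binary event rates (proportions) will be reported on a per patient basis". On censoring, SAP 3.1.3 says: "Statistical models that account for censored data may be employed in appropriate circumstances, e.g. for time-to-event outcomes". Protocol 8.4 makes the same statement as a commitment, limited to suitable cases. Both documents allow Cox regression for predictors of the primary endpoint.
- **One-year endpoint.** Secondary endpoint 11, in palliated patients, is "absence of reinterventions for the management of biliary obstructive symptoms from stent placement to 1 year after stent placement".

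**The concern.** The listed dates do not reliably reach the end of observation. A palliated patient who dies of progression at month 10 without a reintervention may have nothing on the list after the transition visit. A similar patient with a reintervention at month 9 has that date, because reinterventions are on the list. The length of recorded follow-up then depends on whether the event occurred, which is informative censoring.

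The patients exposed are not few. The protocol Introduction cites 25% to 41% of surgical candidates not reaching pancreaticoduodenectomy. Applied to 122 patients, that is 0.25 × 122 = 31 to 0.41 × 122 = 50. At stake are follow-up summaries and any time-to-event estimate of reintervention in this group.

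**Working it through.** **1. The plan's own figure.** No stated figure depends on this date. The nearest is 51 per arm for the primary test. The normal approximation with one-sided alpha 0.05 gives 2 × 0.805 × 0.195 × (1.645 + 0.842)² / 0.20² = 48.5, so 49. An exact unconditional test gives 80.5% power at 51. The sample size reproduces, and the last follow-up date is not an input.

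**2. Which analyses the date can move.** A per-patient proportion counts patients with and without a reintervention, so changing the censoring date changes nothing. A Kaplan-Meier or Cox analysis that censors at this date does change.

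**3. Illustration for a Kaplan-Meier analysis.** Inputs:

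- 12-month reintervention risk absent death: 19.5%, which is 1 − 0.805 (SAP 3.1.2), used here as an assumed 1-year risk.
- Transition at 2 to 7 months, the neoadjuvant duration in the protocol Introduction. Central value: 4.
- Median survival 6, 12 and 21 months. The 21 is from a resectable series in the Introduction; 6 and 12 are assumptions. Central value: 12.
- Constant hazards from stent placement; every reintervention is captured; event-free deaths leave no listed date after the last visit.

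Let λ be the reintervention hazard, μ the death hazard and s = λ + μ. If event-free decedents are censored at the visit that opens an interval of length w, the Kaplan-Meier survival factor for that interval is

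e^(−sw) / [e^(−sw) + (λ/s)(1 − e^(−sw))].

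Central case:

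- λ = −ln(0.805)/12 = 0.01808; μ = ln 2/12 = 0.05776; s = 0.07584; λ/s = 0.2384.
- Monthly interval: 0.9270 / (0.9270 + 0.2384 × 0.0730) = 0.9816. Four of them: 0.9283.
- Months 4 to 12: 0.5451 / (0.5451 + 0.2384 × 0.4549) = 0.8341.
- Risk under the SAP date: 1 − 0.9283 × 0.8341 = 22.6%, against 19.5% when censoring at death. The excess is about 3 points.

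A simulation of 400,000 patients that also included the week 1 visit gave 22.5% against 19.4%. In it, 45.6% of patients died event-free within the year and lost 2.2 months of follow-up each on average.

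Excess in percentage points, same formula:

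| Transition | Median survival 6 months | 12 months | 21 months |
|---|---|---|---|
| Month 2 | 10.7 | 4.7 | 2.5 |
| Month 4 | 6.9 | 3.1 | 1.7 |
| Month 7 | 3.0 | 1.4 | 0.8 |
| Monthly visits all year | 1.0 | 0.5 | 0.3 |

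The last row shows that the visit gap after palliation is the main cause.

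**4. What adding the death date does not do.** Cumulative incidence with death as a competing event is (λ/s)(1 − e^(−12s)) = 0.2384 × (1 − 0.4025) = 14.2%. Censoring at death gives 19.5%. That gap of about 5 points comes from how death is treated, not from the date list.

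**The case against.** The strongest reply is that SAP 7.3 only defines a date. Nothing makes it the censoring time, no 1-year Kaplan-Meier estimate is named, time to reintervention is not a listed endpoint, and the SAP makes censored-data models optional. A reader might infer that patients will be censored at this date and that the reported 1-year risk, endpoint 11 included, will be overstated. The documents do not support that. Endpoint 11 is a yes/no outcome and binary rates are per patient. The rule would matter there only if it also decided who is evaluable at 1 year, which is not stated. The primary endpoint is binary too, and ends at surgery or transition with monthly visits until then. This part of the reply stands.

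Two further objections stand in part. If all SAEs are reported, a fatal one leaves an adverse event date, although the plan does not say that this is the date of death; the protocol's own passages conflict on whether unrelated events are collected. The direction also assumes that reinterventions between the last visit and death are known. After palliation, protocol section 6 leaves stent failure to standard of practice with no new study stent, so some may be missed. In that case last contact is the sounder censoring date, and moving to the death date could understate risk. The same applies to withdrawal.

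A reader might also infer a bias between arms if deaths differ. The documents give no reason to expect that, and no between-arm effect was calculated.

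The reply does not dispose of the point. The protocol commits to censored-data methods where they fit, both documents name Cox regression, and a programmer would have no other end date to use.

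**Conclusion.** The omission is in the text and conflicts with protocol 7.13. It is a stated rule that can give the wrong date, not merely missing detail. Its effect is conditional: if a time-to-event or follow-up-duration analysis uses this date, and reinterventions are captured up to death, follow-up in palliated patients would be understated and Kaplan-Meier reintervention risk overstated. The excess is about 3 points in the central case and 0.8 to 10.7 points across the table's transition times of 2 to 7 months. These sizes rest on assumed survival, constant hazards and no listed date for deaths, so they are illustrations and not forecasts. The per-patient proportions and the primary test are essentially unaffected. The point is worth settling before analysis, but it concerns supporting results.

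**What to change.** In SAP 7.3:

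1. Add date of death, date of withdrawal and date of last documented contact to the list.
2. State that the resulting date ends observation in time-to-event analyses, and name those analyses.
3. Use the death date only where reintervention status is known up to death, and last contact otherwise; treat withdrawal likewise. This condition must be written out, because under a latest-of rule the death date would otherwise always be chosen.
4. For reintervention to 1 year in palliated patients, report cumulative incidence with death as a competing event beside the per-patient proportion.

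The protocol's statements on collecting all SAEs and on not collecting unrelated events should also be reconciled, since they decide which deaths leave a date.

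The cost is a few sentences, a small extra analysis, and the work of confirming reintervention status at death or exit. The documents describe no exit form, so the sponsor should check that these dates are captured.
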